STATISTICAL ANALYSIS PLAN FOR
“The Effect of Physician Ownership on Dialysis Outcomes”

PROTOCOL ID: HS-18-00530-1

SECONDARY ID: K08DK118213

Version #2

Last Modified: 3/11/2021

PI: [name], MS

Keck School of Medicine of the University of Southern California

ANALYTIC DATASETS

Facility level dataset

- 1) Merge the physician ownership dataset with DFC
 - a. Primarily use 2017 data, but if a facility is missing data, salvage with 2018, 2016, 2015 years
- 2) Merge zip codes with census / ACS characteristics
- 3) Merge with the facility survey (from 2017)
- 4) Restrict to free-standing facilities where $\leq 15\%$ of patients in 2017 were pediatric (< 18 years old)
- 5) Variables of interest
 - a. Facility Characteristics
 - i. Profit status
 - ii. Chain vs. independent
 - iii. Size of facility (Number of patients)
 - iv. Staff : patient ratio
 - v. ESRD Network
 - b. Outcomes
 - i. All quality measures from DFC dataset
- 6) Get distribution of patient characteristics for each facility
 - a. Link each facility to a patient
 - i. To assign a patient to a facility, first identify all dialysis patients with at least one month of dialysis in all of 2017 and meeting all of the following criteria
 1. Adults with valid 2728 form
 2. In the USA.
 3. Has Medicare FFS for that month of dialysis
 - ii. If a patient has multiple facilities, assign that patient to the facility that holds the plurality share
 - iii. If there are still ties in facilities, use the first observed facility that has the plurality
 - b. For each patient, for the first observed month of dialysis, get:
 - i. Age, Gender, Race, Ethnicity, Payer, Dual-Eligible (if Medicare)
 - ii. Dialysis modality
 - iii. (Do not exclude any patients for this analysis)
 - c. Collapse back to the facility level, and get counts and % by patient characteristic (for continuous variables like age, we use age brackets, i.e., 18-44, 45-54, 55-64, 65-74, 75+)

Patient-month level dataset / inclusion criteria

- 1) This will be a patient-month dataset
- 2) Identify all patients with at least one month of dialysis in 2017 (Jan-Dec)
- 3) Inclusion criteria
 - a. USA
 - b. Adult in the current month
 - c. Valid 2728 form (2005, 2015 form)

- d. Dialyzing in free-standing facility that has fewer than 15% pediatric
 - i. Only keep if patient can be linked to a valid facility survey and can be linked to the ownership dataset
- 4) Must have Medicare FFS in the current month of dialysis

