 - a. Must have at least 12 months of Medicare FFS prior to the current month
 - b. Create indicator variable for whether the patient-month has had 36+ months of Medicare FFS
- 5) Get patient comorbidities using the CCW algorithm
 - a. Use diagnosis codes from claims in a 12 month lookback
 - b. Sensitivity analysis: use diagnosis codes from claims in a 36 month lookback
- 6) Get the zipcode of residence for that month and merge with the ACS to get zipcode characteristics
- 7) Merge with facility file to get facility characteristics + DFC outcomes (we call these facility level outcomes)
- 8) Covariates of interest:
 - a. Patient level
 - i. Age
 - ii. Sex
 - iii. Race
 - iv. Ethnicity
 - v. Whether patient had a transplant previously
 - vi. Whether the patient is incident (within the first 120 days of ESRD)
 - vii. Number of years with ESRD
 - viii. Comorbidities using CCW algorithm
 - b. Facility characteristics
 - i. Profit status
 - ii. Chain vs. independent
 - iii. Size of facility (Number of patients)
 - iv. Staff : patient ratio
 - v. ESRD Network
 - c. Zipcode Characteristics
 - i. Median income
 - ii. High school graduation rate
 - iii. % below poverty
 - d. Monthly level fixed effects (an indicator for each month of the year)
- 9) Patient Level Outcomes
 - a. Whether patient using home dialysis in the month
 - b. Whether patient was receiving dialysis optimally (defined as either peritoneal dialysis, or hemodialysis through an AV fistula or graft)
 - i. Whether patient was using a fistula
 - ii. Whether patient was using a catheter for 3+ months, including the current month (i.e., look back two months to see whether the patient used a catheter in the other two months)
 - c. Get crownweb outcomes (merge with the crownweb dataset by month/year)
 - i. Create an indicator for whether crownweb data missing for that month
 - ii. Hemoglobin < 10

- iii. Hemoglobin > 12
- iv. Calcium > 10.2
- v. Phosphorus > 7
- d. Get other outcomes
 - i. Whether patient died in that month
 - ii. Whether patient was hospitalized that month
 - iii. Whether patient had a hospitalization that month followed by a 30-day readmission
 - 1. Patients are eligible for this only if the patient was discharged alive
 - iv. Whether patient had a hospitalization that month followed by an unplanned 30-day readmission

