 (<https://qualitynet.cms.gov/inpatient/measures/readmission/resources#tab3>, “2018 All-Cause Hospital Wide Measure Updates and Specifications Report Hospital-Level 30-Day Risk-Standardized Readmission Measure – Version 7.0”, pages 51 and 68)
 - v. Whether patient had a blood transfusion that month
 - 1. Criteria 1
 - a. From inpatient, outpatient, SNF claims
 - b. Revenue code 0390 OR 0392 OR 0399 PLUS any of the following HCPCS/CPT
 - i. P9010
 - ii. P9011
 - iii. P9016
 - iv. P9021
 - v. P9022
 - vi. P9038
 - vii. P9039
 - viii. P9040
 - ix. P9051
 - x. P9054
 - xi. P9056
 - xii. P9057
 - xiii. P9058
 - c. Calculate number of units of blood by taking the sum of the units for (Revenue center code 0390 OR 0392 OR 0399) across all line items that correspond to that specific day.
 - i. Sum across all days for a given month
 - 2. Criteria 2
 - a. If Criteria 1 is missing, then determine whether a blood transfusion occurred for the entire claim (assign to the month of the through date of the claim)
 - b. Look for value code 37
 - 3. Criteria 3

- a. If Criteria 1 is missing, then determine whether a blood transfusion occurred for the entire claim (assign to the month of the through date of the claim)
- b. Look for any of the following ICD procedure codes:
 - i. ICD9
 - 1. 9903
 - 2. 9904
 - ii. ICD10
 - 1. 30230H1, -P1, -N1
 - 2. 30233H1, -P1, -N1
 - 3. 30240H1, -P1, -N1
 - 4. 30243H1, -P1, -N1
 - 5. 30250H1, -P1, -N1
 - 6. 30253H1, -P1, -N1
 - 7. 30260H1, -P1, -N1
 - 8. 30263H1, -P1, -N1
- vi. Whether a patient received an ESA and their dose (using CROWNWeb data)
 - 1. Consolidate to Darbepoetin, Erythropoietin alfa, Erythropoietin beta
 - 2. Make sure units are consistent (darbe in mcg, Epo alfa in units, Epo beta in units)
 - 3. Make sure the doses are normalized, to the same mean (i.e., we want to make sure we are looking at relative changes in doses within the same ESA)
 - a. Take the mean doses of each of the ESA types, then divide all the doses by this mean. In other words, all means will be set at “1”
 - 4. For each month of dialysis create the following variables
 - a. Whether ESA administered
 - b. Type of ESA administered
 - c. Dose
 - 5. For each dialysis chain, determine the ESA that is the majority of patient-months

ANALYSES

Facility Level Outcomes

- 1) Use facility level dataset (patient level covariates are collapsed to facility level using summary statistics for that facility)
- 2) Dependent variable (left hand side)

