 - a. Facility level outcomes as specified above
- 3) Independent Variables:
 - a. Whether facility is physician owned

- b. Regression 1: Control only for facility, geographic, and temporal level covariates
- c. Regression 2: Control for patient, facility, geographic, temporal level covariates.
- 4) Models: OLS for continuous outcomes, logit for binary outcomes, robust standard errors

Patient Level Regressions

- 1) Population: patient-month dataset
- 2) Dependent variable (left hand side):
 - a. Patient level outcomes
- 3) Independent variables (right hand side)
 - a. Whether patient is dialyzing in a facility that is physician owned (covariate of interest)
 - b. Covariates above (patient, facility, zipcode, temporal characteristics)
- 4) Models (in order) for all outcomes except blood transfusion and ESA outcomes:
 - a. Logit with patient level fixed effects, non-parametric bootstrap standard errors
 - b. Logit with patient level fixed effects, robust standard errors
 - c. OLS with patient level fixed effects, cluster robust standard errors at facility level
 - d. OLS with patient level fixed effects, robust standard errors
- 5) Models (in order) for whether patient received a blood transfusion
 - a. Outcomes
 - i. Criteria 1 only
 - ii. Criteria 1+2
 - iii. Criteria 1+2+3
 - b. Models
 - i. Logit with patient level fixed effects, non-parametric bootstrap standard errors
 - ii. Logit with patient level fixed effects, robust standard errors
 - iii. OLS with patient level fixed effects, cluster robust standard errors at facility level
 - iv. OLS with patient level fixed effects, robust standard errors
- 6) Models (in order) for # of units of blood transfused
 - a. Outcomes
 - i. Use the number of units of blood detected under Criteria 1. If a blood transfusion detected under Criteria 2 or 3, indicate that the patient received 1 unit of blood
 - ii. Use the number of units of blood detected under Criteria 1. If a blood transfusion detected under Criteria 2 or 3, indicate that the patient received 1 unit of blood. Also include an indicator variable that the patient had a blood transfusion detected under criteria 2 or 3.

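### The hospitalization outcome (9d.ii) counts the kidney-transplant admission as an adverse stay, and the readmission (d.iii) and transfusion (d.v) outcomes do not exclude it either

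*SAP*

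**What the plan says.** All references are to the SAP, section on the patient-month level dataset, unless noted.

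- **Hospitalization, item 9d.ii:** "Whether patient was hospitalized that month". No cause, transplant or planned-stay restriction follows.
- **Readmission, items 9d.iii and 9d.iv:** d.iii counts any 30-day readmission. Its one stated limit on the index stay is "Patients are eligible for this only if the patient was discharged alive". d.iv is "Whether patient had a hospitalization that month followed by an unplanned 30-day readmission" and points to an external specification. This is the only place where the plan separates unplanned stays from others.
- **Transfusion, item 9d.v:** Criteria 1 draws its events "From inpatient, outpatient, SNF claims", with no type of inpatient stay set aside.
- **Transplant, item 8a.v:** "Whether patient had a transplant previously", a covariate. A transplant during the study year is not an outcome, an exclusion or a censoring event.
- **Month eligibility, item 4:** "Must have Medicare FFS in the current month of dialysis", plus the look-back requirement. Nothing removes a month in which dialysis is followed by a transplant.
- **Model (Analyses, Patient Level Regressions, item 4):** the first listed is "Logit with patient level fixed effects, non-parametric bootstrap standard errors". All four listed models carry patient fixed effects.

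**The concern.** Most reasons for admission in dialysis patients point one way: a stay is a bad event, and fewer stays suggest better care. A transplant admission points the other way, because it is a result that a dialysis facility should help to bring about. Item 9d.ii gives both the same code.

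The same stay reaches two further outcomes. In d.iii, a readmission within 30 days of the transplant is charged to a dialysis facility that, if the graft works, no longer treats the patient. In d.v, blood given around the operation counts like a transfusion for poorly managed anemia.

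The exposure is physician ownership. It is plausible, although the SAP does not say so, that ownership bears on transplant referral. If it does, more transplants would appear as more hospitalization, and fewer transplants as less. Covariate adjustment cannot remove this, because the fault lies in how the outcome is defined.

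**Working it through.** **Inputs.** The SAP states no hospitalization rate, transplant rate, planned share or sample size, so there is no figure of its own to reproduce. All rates below are assumptions:

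- monthly probability of a non-transplant stay, h: 8% to 16%, central value 12%;
- monthly probability of a transplant, t: 0.1% to 0.6%, central value 0.3%;
- ratio of transplant rates by ownership, RR: 1 to 2.

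**Step 1: share of hospitalized months.** With the two kinds of stay independent, P(any stay) = 1 − (1 − h)(1 − t). At the central values this is 1 − 0.88 × 0.997 = 0.1226, and the transplant share is 0.003 / 0.1226 = 2.4%. Over the full ranges it is about 0.6% to 7%.

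**Step 2: contrast without fixed effects.** With other stays equal by ownership, the spurious difference is (1 − h) × t × (RR − 1).

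| RR | Calculation | Difference, percentage points | Odds ratio |
|---|---|---|---|
| 1.5 | 0.88 × 0.003 × 0.5 | 0.13 | 1.012 |
| 2 | 0.88 × 0.003 × 1.0 | 0.26 | 1.025 |

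For RR from 1.25 to 2 over all assumed rates, the odds ratio runs from 1.002 to 1.07. Leaving the transplant stay out returns it to 1.00.

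**Step 3: contrast in the kind of model planned.** Patient fixed-effects OLS with month effects (item 8d) was simulated at h = 12% and t = 0.3%, with follow-up ending at transplant. Some patients change ownership type during the year; 10% is the assumed share. The shift is the ownership coefficient with transplant stays counted, minus the coefficient without them.

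| Transplant rate ratio | Shift, percentage points |
|---|---|
| 1 | about 0 |
| 1.5 | 0.07 to 0.12 |
| 2 | 0.18 to 0.24 |

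Fixed effects reduce the shift somewhat but do not remove it.

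**Step 4: who produces the shift.** In a simulation without month effects, doubling the transplant rate only among patients who never change ownership type left the gap practically unchanged (0.06 against 0.07 percentage points). Doubling it for everyone under physician ownership raised the gap from 0.09 to 0.30. The shift therefore comes through patients who change ownership type. The non-zero gap at equal rates arises because a transplant ends follow-up and so falls in the last facility; with month effects it is about 0.

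**Step 5: scale.** A 5% relative effect on 12% is 0.05 × 12 = 0.6 percentage points. A shift of 0.1 to 0.2 points is 17% to 33% of that.

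**Step 6: other planned stays.** If ownership lowers unplanned stays by 5% and leaves planned stays alone, the all-cause ratio is (1 − s) × 0.95 + s. For a planned share s of 5% to 15% this gives 0.9525 to 0.9575, so 5% to 15% of the effect is diluted (0.0025/0.05 to 0.0075/0.05).

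**The case against.** All-cause hospitalization is a legitimate and common outcome. The SAP never names unplanned admission as its target, and splitting readmissions into any and unplanned does not oblige the same split for admissions. That stands. It is why all-cause should remain the result, and why an unplanned version belongs beside it and not in its place.

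Three stronger readings are tempting, and the SAP does not support them.

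- **A facility with many transplants is scored as worse.** No facility is scored on d.ii. It is the dependent variable in patient-month regressions with patient fixed effects, so a plain comparison between facilities is not what is estimated. Ownership has to matter to the same patient's chance of transplant between months of 2017, which is a narrower pathway.
- **Counting planned stays hides a quarter to three quarters of an effect on unplanned stays.** That needs ownership to raise planned stays by 20% while lowering unplanned stays by 5%: the ratio is then (1 − s) × 0.95 + s × 1.20, about 0.96 to 0.99. Nothing in the SAP suggests such a rise. If it occurred, the ratio would report the all-cause effect correctly.
- **The transplant stay is an index stay for d.iv.** The external specification cited there may restrict index stays, and it cannot be checked from the SAP. The point is firm only for d.iii.

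Two further limits hold. The SAP does not define how much dialysis makes a month of dialysis, so keeping the transplant month is an inference from the absence of a rule. For d.iii and d.v the stay does not set the outcome by itself: a readmission or a transfusion must also occur, and no size is offered for either.

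**Conclusion.** The point holds in a limited form. As written, d.ii counts a kidney-transplant admission in a month with earlier dialysis as an adverse stay, d.iii accepts it as an index stay, and d.v counts transfusions on it. Patient fixed effects do not neutralize this.

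The bias is small: about 0.1 to 0.2 percentage points for a 1.5- to 2-fold difference in transplant rates, at the assumed 12% and 0.3% per month. It is about zero if transplant rates do not differ by ownership, and it arises through patients who change ownership type. Because the SAP gives no rates, the actual size and sign are unknown. This is a cheap improvement to an outcome definition; it does not invalidate the hospitalization analysis.

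**What to change.** - **d.ii:** do not count the admission for kidney transplant. Score the month on its other stays.
- **d.iii:** drop that admission as an index stay. Do the same in d.iv unless the cited specification already does so, and say which applies.
- **d.v:** do not count transfusions, or units, given on that stay, under any of the three criteria.
- **Reporting:** keep all-cause hospitalization, without the transplant stay, as the result. Report unplanned hospitalization beside it, mirroring d.iii and d.iv.

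The cost is a few lines of SAP wording, minor extra coding and slightly fewer events. Item 8a.v already calls for transplant information, but the SAP does not say whether dates come with it, so the source used to identify the stay should be named. d.iv already needs a planned/unplanned rule; whether it carries over unchanged from readmissions to admissions should be confirmed against the cited specification.

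### The live-discharge rule is written for all-cause but not unplanned 30-day readmission, neither outcome has a stated risk set, and no Medicare FFS is required after the index month

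*SAP*

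**What the plan says.** All the relevant text is in the SAP, under the patient-month dataset and the patient-level regressions.

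- **Item 9.d.iii** defines the all-cause outcome: "Whether patient had a hospitalization that month followed by a 30-day readmission". Its only sub-item reads "Patients are eligible for this only if the patient was discharged alive".
- **Item 9.d.iv** is a separate outcome at the same level: "Whether patient had a hospitalization that month followed by an unplanned 30-day readmission". It has no eligibility sub-item. It points to pages 51 and 68 of the "2018 All-Cause Hospital Wide Measure Updates and Specifications Report" without saying what is taken from them.
- **Item 4** of the inclusion criteria: "Must have Medicare FFS in the current month of dialysis". **Item 4a**: "Must have at least 12 months of Medicare FFS prior to the current month". **Item 4b** only adds a flag: "Create indicator variable for whether the patient-month has had 36+ months of Medicare FFS". No item requires FFS after the index month.
- **Patient Level Regressions, item 1**, names the patient-month dataset as the population for every patient-level outcome. No outcome-specific subset is given there.

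**The concern.** A 30-day readmission outcome needs an index stay, a live discharge and a follow-up window in which a readmission would be seen. The SAP states the second for one of two paired outcomes and does not secure the third for either.

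**Risk set.** The live-discharge rule is nested under iii and refers to that outcome alone. If iv is programmed as printed, on the full patient-month dataset, two kinds of month that cannot produce a readmission score 0: months without an admission, and months whose admission ended in death. Item iv would then mix admission frequency with readmission risk. An ownership effect on hospitalization, already outcome 9.d.ii, could reappear as an effect on unplanned readmission, and deaths in hospital would count as favourable results. A gap between iii and iv could be misread as a difference between planned and unplanned readmissions.

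**Follow-up.** The FFS inclusion rule implies that hospital stays are read from FFS claims. If coverage ends during the 30 days after discharge, a later readmission leaves no claim and, with no rule to the contrary, is scored as none. The SAP does plan for missing laboratory data, with the CROWNWeb indicator in item 9.c.i, but has no counterpart here.

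**Working it through.** The SAP gives no event rate, coverage-loss rate or sample size on this point, so there is no figure of its own to reproduce. The calendar count in step 1 needs only the 2017 calendar. Every rate in steps 2 to 4 is an assumption.

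**1. How often the window leaves the index month.** Let the window be the 30 days after discharge. For a discharge on day *d* of a month with *L* days, the days falling after the month are min(30, max(0, *d* + 30 − *L*)).
- The window stays inside the month only if *d* + 30 ≤ *L*, that is, day 1 of a 31-day month. That is 7 dates, so 365 − 7 = 358 dates (98.1%) run over.
- Days outside the index month: seven 31-day months give 7 × 465 = 3,255; four 30-day months give 4 × 465 = 1,860; February gives 462. The total is 5,577 of 365 × 30 = 10,950, or 51%.
- For December, 30 of 31 discharge dates have a window running into 2018.

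**2. What the missing coverage rule could cost.** Assume a true readmission risk of 30%, and that a share *f* of patients loses FFS at the end of the index month. Observed risk ≈ 0.30 × (1 − 0.51 × *f*).
- *f* = 0.5%, 1%, 2% gives about 29.9%, 29.8%, 29.7%.

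**3. In-hospital deaths kept as non-events.** Assume 30% of live discharges are readmitted and a share *q* of hospitalized patient-months ends in in-hospital death. Risk among hospitalized months = 0.30 × (1 − *q*).
- *q* = 2%, 5%, 10% gives 29.4%, 28.5%, 27.0%.

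**4. Effect on the ownership contrast, by reading.** Assume a share *h* = 8–16% of patient-months has an admission, 96% of these are discharged alive in both groups, *r* = 15–35% of live discharges are readmitted in both groups, and physician ownership lowers admissions by 10%. The same *r* range is used for both outcomes. These are simple odds ratios for two groups, not fixed-effects estimates.

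| Reading | Item iii | Item iv |
|---|---|---|
| A. iii on live discharges only; iv on all patient-months | 1.00 | 0.895–0.899 |
| B. Both on hospitalized months; iv keeps in-hospital deaths as 0 | 1.00 | 1.00 |
| C. Both on all patient-months; iii drops only months with in-hospital death | about 0.90 | about 0.90 |

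- **A, item iv:** *p*₀ = *h* × 0.96 × *r* and *p*₁ = 0.9 × *p*₀. At *h* = 0.08, *r* = 0.15: *p*₀ = 0.01152, *p*₁ = 0.010368, OR = 0.899. At *h* = 0.16, *r* = 0.35: *p*₀ = 0.05376, *p*₁ = 0.048384, OR = 0.895.
- **B, item iv:** the risk is 0.96*r* in both groups, so OR = 1.00.
- **C:** item iv is as in A. Item iii differs only by removing 0.04 × *h* = 0.3–0.6% of patient-months, so it too carries the admission effect.

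**The case against.** The strongest reply is that iii and iv share the same stem and differ only in the word for unplanned, so the live-discharge condition was probably meant to define a valid index stay for both. A death in hospital cannot be followed by a readmission, so the numerator of iv is unaffected. The citation at iv may also bring in cohort rules, including live discharge. All of this is fair. The cited pages are not at hand, so it can be neither confirmed nor excluded, and the supportable statement is that the risk sets *may* differ. A programmer working from the SAP still cannot tell, because the condition is spelled out for one outcome and left to an unspecified part of an outside report for the other.

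It can also be said that 0.90 does not measure the missing live-discharge rule. That is right. Readings B and C remove the contrast between iii and iv; the 0.90 comes from how months without an admission are coded. That question is open for both outcomes, and under C both inherit the admission effect.

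On coverage, the 51% is a share of calendar days and not a loss of data. A patient who keeps FFS is fully observed, nothing in the SAP says that 2018 claims are unavailable, and no mechanism is given for coverage loss to differ by ownership. This limits the size of the point, but the missing rule remains.

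Finally, a monthly indicator of admission followed by unplanned readmission is a legitimate outcome in itself. If that is intended, the SAP should say so for both items, so that it is not read as readmission risk after discharge.

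**Conclusion.** The point holds as a defect in how the two readmission outcomes are specified, and it should be corrected. The live-discharge rule is attached to one outcome only, the coding of months without a hospitalization is unstated for both, and no coverage is required in the window where the outcome occurs.

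Three stronger inferences are tempting and unsupported:

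- A reader might infer that the denominators definitely differ. The shared wording and the citation leave that open.
- A reader might infer that FFS is required in the index month alone. Item 4a also requires at least 12 prior months; what is absent is any requirement afterwards.
- A reader might infer a bias of 10% in the odds ratio. The value of about 0.90 arises as a discrepancy between the outcomes only under reading A with the assumed rates. Under B, with equal live-discharge shares, both odds ratios are 1.00.

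The coverage gap touches nearly every discharge date (358 of 365), but its effect is probably small: an assumed FFS loss of 0.5–2% moves 30% to between 29.7% and 29.9%. The true loss rate is not in the SAP. The risk set is the larger issue, because it decides whether these outcomes measure readmission risk or partly repeat hospitalization.

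**What to change.** Move the live-discharge rule up so that it governs both outcomes, and extend it to coverage, for example:

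> For iii and iv, the analysis set is patient-months with a hospitalization from which the patient was discharged alive, with Medicare FFS through 30 days after discharge or until death, if earlier.

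This excludes months without a hospitalization from both outcomes, settles the handling of in-hospital deaths, and secures the follow-up window.

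Beside the citation at 9.d.iv, state that the cited pages are used only to classify readmissions as planned or unplanned, or name any other rule taken from them.

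The cost is a few lines of SAP text and one denominator filter. A few index discharges are lost where FFS ends within 30 days.

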 - iii. Use the number of units of blood detected under Criteria 1. If a blood transfusion detected under Criteria 2 or 3, indicate that the patient received 1 unit of blood. Also include an indicator variable that the patient had a blood transfusion detected under criteria 2 or 3 AND interact this indicator variable with the covariate for whether patient dialyzed in a facility that is physician owned.
 - b. Models

- i. Poisson with patient level fixed effects, non-parametric bootstrap standard errors
 - ii. Poisson with patient level fixed effects, robust standard errors
 - iii. OLS with patient level fixed effects, cluster robust standard errors at facility level
 - iv. OLS with patient level fixed effects, robust standard errors
- 7) Models (in order) for dose of ESA received
 - a. Poisson with patient level fixed effects, non-parametric bootstrap standard errors
 - b. Poisson with patient level fixed effects, robust standard errors
 - a. OLS with patient level fixed effects (dose of ESA received), cluster robust standard errors at facility level
 - i. Include covariate for chain
 - b. OLS with patient level fixed effects (dose of ESA received), robust standard errors
 - i. Include covariate for chain
 - c. Split dataset into 3 separate datasets based on CHAIN of assigned dialysis facility. Specifically, assign each chain to the type of ESA that takes up the majority of all patient-months. Separately, run the following regression on each of the datasets
 - i. Poisson with patient level fixed effects, non-parametric bootstrap standard errors
 - ii. Poisson with patient level fixed effects, robust standard errors
 - iii. OLS with patient level fixed effects (dose of ESA received), cluster robust standard errors at facility level
 - iv. OLS with patient level fixed effects (dose of ESA received), robust standard errors

Subgroup analyses

- 1) Repeat the above regressions, but this time we have the following independent variables of interest (we also include all the other adjusters)
 - a. Whether facility is physician owned (phys_own)
 - b. Whether facility is LDO owned (ldo_own)
 - c. Interaction term between these two (phys_own#ldo_own)
- 2) In addition to reporting the coefficients for these 3 terms, we also care about the following comparisons:
 - a. FOR FACILITIES THAT ARE LDO OWNED: effect of physician ownership
 - i. The parameter of interest is the sum of the following coefficients:
 $\text{phys_own} + \text{phys_own}\#\text{ldo_own}$

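### Most main models adjust for chain only as chain versus independent, so the pooled physician-ownership coefficient can be confounded by LDO status, and no planned model gives an LDO-adjusted overall effect

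*SAP*

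**What the plan says.** The facility covariates are listed twice in the SAP, under Facility level dataset, item 5)a, and under Patient-month level dataset, item 8)b. Both lists hold the same five items. Two describe how the facility is organised: "Profit status" and "Chain vs. independent". The others are size, staffing ratio and ESRD Network. LDO ownership is in neither list.

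The main models draw on these lists:

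- Facility Level Outcomes, item 3): "Regression 1: Control only for facility, geographic, and temporal level covariates". A second regression adds patient covariates.
- Patient Level Regressions, item 3)b: "Covariates above (patient, facility, zipcode, temporal characteristics". Every model there has patient fixed effects, for example "OLS with patient level fixed effects, cluster robust standard errors at facility level".

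LDO status first appears under Subgroup analyses, item 1)b: "Whether facility is LDO owned (ldo_own)". There all regressions are run again with physician ownership, LDO ownership and their interaction, keeping the other adjusters. The ownership effect is then reported separately for LDO and non-LDO facilities.

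ESA dose is treated differently (Patient Level Regressions, item 7). The pooled OLS models add a chain covariate that the SAP does not define, and further models split the data into three by each chain's majority ESA. The pooled Poisson models for ESA dose list no such addition.

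**The concern.** A two-level chain flag assumes that, after the other adjusters, an LDO facility and a small-chain facility are exchangeable. The plan does not treat them so elsewhere: it defines an LDO variable and lets the ownership effect differ by it. If physician ownership is more or less common in LDOs than in small chains, and LDO care goes with different outcomes, the main ownership coefficient takes up part of that difference. A pooled ownership effect could then appear where none exists, or a real one could be masked.

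There is also a problem of interpretation. The subgroup models bring in the LDO main effect and the interaction in one step. If the main estimate and the two stratum estimates disagree, the planned output cannot show whether the cause is confounding by LDO status or a true difference in effect between strata.

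**Working it through.** The SAP states no figure on this point, so there is nothing of the plan's own to reproduce. The check has two parts.

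**1. Which models hold LDO status**

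| Models | Chain information | LDO status |
|---|---|---|
| Facility-level Regressions 1 and 2 | two-level flag | no |
| Patient-level models outside ESA dose | two-level flag | no |
| ESA dose, pooled Poisson | two-level flag | no |
| ESA dose, pooled OLS | flag plus undefined chain covariate | absorbed if this means chain identity |
| ESA dose, split by chain's majority ESA | flag, within three datasets | not entered; split by chain |
| Subgroup repeat of all regressions | as in the model repeated | LDO main effect plus interaction |

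No row has physician ownership and LDO ownership entered together without the interaction, except possibly the ESA-dose OLS row.

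**2. Illustration of size (every input is an assumption)**

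Linear outcome; true ownership effect 0; facility mix 70% LDO, 18% small chain, 12% independent; LDO effect on the outcome γ = 5 points; no other adjusters.

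With ownership and the chain flag in the model, the spurious coefficient is

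bias = γ × d × w,

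where d is the LDO share among owned chain facilities minus that among non-owned chain facilities, and w is the chain stratum's share of the within-stratum variance of ownership. Independent facilities contribute no bias and dilute it.

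Worked case, ownership 30% in LDO and 50% in non-LDO facilities:

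- Owned: 0.70 × 0.30 = 0.21 LDO and 0.18 × 0.50 = 0.09 small chain; LDO share 0.21/0.30 = 0.700.
- Not owned: 0.49 LDO and 0.09 small chain; LDO share 0.49/0.58 = 0.845.
- d = 0.700 − 0.845 = −0.145.
- Ownership among chains 0.30/0.88 = 0.341; chain weight 0.88 × 0.341 × 0.659 = 0.198; independent weight 0.12 × 0.50 × 0.50 = 0.030; w = 0.198/0.228 = 0.868.
- bias = 5 × (−0.145) × 0.868 = −0.63 point.

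The same formula gives the third column below. The simulations used 400,000 units cross-sectionally, and 20,000 patients over 12 months, each changing facility once, for the fixed-effects runs. Entries are absolute sizes in points; ranges cover γ = +5 and −5.

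| Ownership, LDO vs small chain | d | Formula | Simulated, no fixed effects | Simulated, patient fixed effects |
|---|---|---|---|---|
| 30% vs 30% | 0 | 0 | 0.01–0.03 | 0.02–0.08 |
| 30% vs 40% (independent 50%) | −0.075 | 0.32 | 0.29–0.36 | not run |
| 30% vs 50% | −0.145 | 0.63 | 0.62–0.63 | 0.48–0.70 |
| 20% vs 60% | −0.322 | 1.38 | 1.41 | 1.37–1.42 |
| 50% vs 30% | +0.131 | 0.59 | 0.52–0.61 | not run |

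The sign follows the product γ × d, so it can go either way. Adding LDO ownership as a main effect brought the coefficient back to within about 0.1 point of 0 in every run. The planned interaction model, checked without fixed effects, gave 0 to within about 0.15 point in both strata.

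Patient fixed effects remove stable patient traits. The ownership coefficient is then identified by patients whose facility's ownership status changes, and LDO status can change in the same move.

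**The case against.** The strongest reply is that the plan already contains LDO-adjusted estimates for every regression: "Repeat the above regressions, but this time we have the following independent variables of interest (we also include all the other adjusters)". Because the chain flag stays in, those models separate LDO, non-LDO chain and independent facilities. In the illustration they recover the true null in both strata, so a pooled effect with nothing behind it in either stratum would show in the planned output. The SAP also does not rank the subgroup results below the others. This stands, and it limits the damage. It does not supply an LDO-adjusted overall effect, and it leaves confounding and effect modification entangled when the results differ.

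Three further replies have some force. The ESA-dose OLS and chain-split models go beyond the flag, so the point does not reach them in the same way. Profit status, size, staffing and Network may absorb part of any LDO difference. In the patient-level models, what matters is how LDO and ownership status change together among patients who move, and the fixed-effects runs rest on assumed switching patterns.

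A reader might infer that the main ownership contrast is in fact confounded. The SAP does not support that. Bias needs LDO status to be associated with both ownership and the outcome, given the other adjusters, and the document gives neither association. With equal ownership shares the bias is about zero.

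**Conclusion.** The main models outside the ESA-dose OLS and chain-split analyses leave LDO and non-LDO chain facilities in one adjustment level, so residual confounding of the pooled ownership coefficient by LDO status is possible. It is not demonstrated. Patient fixed effects do not exclude it, and the subgroup models expose it only in part.

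Size and direction are unknown from the document. The illustrative 0 to 1.4 points depends on an assumed 5-point LDO effect, an assumed facility mix and assumed ownership shares, in a linear model with no other adjusters. For binary outcomes the plan's first-listed model is a logit, where these figures do not carry over directly. Simply multiplying the difference in LDO share by the outcome gap overstates the linear bias, because it ignores the independent facilities: at 20% versus 60% it gives 0.322 × 5 = 1.6 points against 1.4 from the regression.

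**What to change.** In both covariate lists (Facility level dataset, item 5)a.ii; Patient-month level dataset, item 8)b.ii), replace the two-level item with three levels: LDO, non-LDO chain, independent. Adding the LDO indicator to the main covariates beside the existing flag is equivalent. All main models then inherit it through the existing references to the lists, and the subgroup models differ from them only by "Interaction term between these two (phys_own#ldo_own)". A difference between main and subgroup results can then no longer come from leaving the LDO main effect out of the main models.

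The cost is a wording change in two places, one extra parameter per model and possibly a small loss of precision. The variable is already needed for the subgroup analysis.
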